ассо
3

Once complete, upload this form as a Word document to the IRB Protocol Management System:

https://secure.research.vt.edu/irb_Section 1: General Information

1.1 DO ANY OF THE INVESTIGATORS OF THIS PROJECT HAVE A REPORTABLE CONFLICT OF INTEREST? (http://www.irb.vt.edu/pages/researchers.htm#conflict)

No Yes, explain: □	
1.2 WILL THIS	RESEARCH INVOLVE COLLABORATION WITH ANOTHER INSTITUTION?
□ No, go to questio	on 1.3
Yes, answer ques	tions within table
	IF YES
	Provide the name of the institution [for institutions located overseas, please also provide name of country]: Carilion Hospital
	Indicate the status of this research project with the other institution's IRB:
	☐ Pending approval
	☐ Other institution does not have a human subject protections review board
	oximes Other, explain: Human subject activities covered in this protocol.
	Will the collaborating institution(s) be engaged in the research? (http://www.hhs.gov/ohrp/policy/engage08.html)
	⊠ No
	☐ Yes
	Will Virginia Tech's IRB review all human subject research activities involved with this
	project? \square No, provide the name of the primary institution:
	⊠ Yes
	Note: primary institution = primary recipient of the grant or main coordinating center

1.3 IS THIS RESEARCH FUNDED?

	IF YES	
	Provide the name of the sponsor [if NIH, specify department]: NIH/National Institute on Drug Abuse	9
	□ No	
	⊠ Yes	
	If yes,	
	☐ No, all human subject activities are covered in this IRB application	
	☐ Yes, however these activities will be covered in future VT IRB applications, these activities include:	
	☐ Yes, however these activities have been or will be reviewed by another institution's IRB, the name of	
	☐ Other, explain:	
	Is Virginia Tech the primary awardee or the coordinating center of this grant?	
	☐ No, provide the name of the primary institution:	
	⊠ Yes	
4 DOES T	THIS STUDY INVOLVE CONFIDENTIAL OR PROPRIETARY INFORMATION (OTHER	_
OR NATIO	MAN SUBJECT CONFIDENTIAL INFORMATION), OR INFORMATION RESTRICTED ONAL SECURITY OR OTHER REASONS BY A U.S. GOVERNMENT AGENCY? For ernment / industry proprietary or confidential trade secret information	
nstitute on l igarettes,	De: This project uses investigational reduced nicotine cigarettes manufactured by the National Drug Abuse for use in resarch studies. NIDA holds the proprietary master file for these and their use in research studies needs to be approved by the FDA Center for Tobacco Products. Exercisely, any serious adverse events that occur with these products will be reported to the FDA.	
	•	

1.5 DOES THIS STUDY INVOLVE SHIPPING ANY TANGIBLE ITEM, BIOLOGICAL OR SELECT

AGENT OUTSIDE THE U.S?

⋈ No

□ Yes

Section 2: Justification

2.1 DESCRIBE THE BACKGROUND, PURPOSE, AND ANTICIPATED FINDINGS OF THIS STUDY:

Abuse liability of reduced nicotine content cigarettes: Purchasing and e-cigarette substitution IRB v.4
09/15/2021

With the recently acquired mandate of the FDA to regulate the rapidly increasing market of tobacco products, research that can inform these regulations is vital. Before modifying the tobacco product marketplace through regulatory action, it is important to understand how specific features of tobacco products influence the choices to purchase and consume that product. The long-term goal of this line of research is to build an evaluative framework to assess how different aspects of tobacco products that may be subject to regulatory action (e.g., flavor, nicotine content, packaging) influence decisions to purchase and consume those products across a range of prices. To craft effective regulations, it is important to understand how specific features of tobacco products that may be subject to regulatory action influence the choice to purchase and consume that product.

Economic demand analyses quantify the relationship between the cost of a commodity and population-level measures of consumption of that commodity. Behavioral economic demand analyses are analogous to these population-level analyses, but can be used to understand the level of motivation to consume a product on either an individual or small group level, including cigarettes (Bickel et al., 1995; MacKillop et al., 2008). This level of analysis allows for experimental manipulations to be made on variables of interest. By quantifying how consumption decreases as costs to obtain and consume a product increase, important indices of demand are obtained. These indices can be grouped into two main measures of consumption, demand intensity and demand elasticity, which are associated with use level and dependence severity (MacKillop et al., 2008, 2009, 2010; Murphy et al., 2011). Demand intensity is the amount of the commodity consumed when available at a very low cost approaching free, and demand elasticity quantifies the degree to which the individual is willing to increase monetary or effort-based expenditures to maintain the same level of consumption as costs increase. Elasticity of demand has been shown to be a characteristic of the drug itself and independent of drug dose for many drugs including nicotine (Bickel et al., 1991; Hursh & Roma, 2013; Hursh & Silberberg, 2008; Hursh & Winger, 1995).

A fundamental observation of economics is that the type and number of products in a marketplace can alter a commodity's demand elasticity as well as the type and degree of interaction among those products. As a result, the ability to achieve the tobacco control goals of reducing the consumption of a particular product may be enhanced or diminished via the economic processes of substitution and complementarity (see Bickel, DeGrandpre, et al., 1995 for a review). Substitution, complementarity, and independence are measured by cross-price elasticity of demand and are represented by elasticity slopes that are positive, negative, or near zero, respectively. Studies to date have almost exclusively examined only pairs of products and in very few cases three concurrent commodities. Relevant to this application, the investigators examined the interaction of three commodities in one of their prior studies (Johnson, et al., 2004). Specifically, smokers had access to conventional cigarettes, reduced-nicotine cigarettes, and nicotine gum. When the price of conventional cigarettes increased, consumption of both reduced-nicotine cigarettes and nicotine gum increased even though their prices were fixed. Thus, reduced-nicotine

cigarettes and nicotine gum functioned as substitutes for conventional cigarettes. Indeed, by concurrently using both products, the smoker could reproduce different aspects of the conventional cigarette experience by consuming the reduced-nicotine cigarette (i.e., sensory effects associated with combustible tobacco smoke inhalation) and nicotine gum (i.e., central effects associated with nicotine ingestion). Importantly, reduced-nicotine cigarettes functioned as a better substitute than gum when each was offered as a substitute alone (the use of denicotinized cigarettes increased the most).

To inform how various products may interact, we have developed and tested a novel method called the Experimental Tobacco Marketplace. The Experimental Tobacco Marketplace is a systematic extension of similar marketplace methods used with other consumer products (e.g., food marketplaces used in obesity and other nutrition-related research; Epstein, Dearing, Roba, & Finkelstein, 2010). In experimental

marketplaces, multiple products are available and the experimenter controls the prices for each. These marketplaces can be either physical or virtual stores (similar to online retailers) and permit the examination of demand elasticity and intensity and degree of substitution or complementarity in consumer behavior under conditions that approximate naturalistic settings.

This study will extend findings from an ongoing project examining the effects of different concentrations of nicotine in cigarettes (0.4mg/g, 1.4mg/g, 2.5mg/g, 5.6mg/g, 17.4mg/g) on laboratory behavioral economic demand measures by including nicotine pouches (a novel product) and utilizing a within-subjects design. Employing this innovative Experimental Tobacco Marketplace, we propose to examine 2 concentrations of reduced-nicotine cigarettes (0.4 mg/g, 17.4mg/g) and tobacco-free nicotine pouches (2 mg and 8 mg). We will use a within-subjects design to allow smokers to sample each of the high dose and low dose cigarettes as well as a high dose and low dose of commercially available tobacco-free nicotine pouches. After sampling, participants will complete one Experimental Tobacco Marketplace session under four conditions: 1) increasing prices for the 0.4 mg/g cigarette with no other products available; 2) increasing prices for the 17.5 mg/g cigarette with no other products available; and 4) increasing prices for the 17.5 mg/g cigarette with other products available. The results of this experiment will be valuable in determining the degree and extent to which cigarette smokers may switch to a harm reduction alternative.

2.2 EXPLAIN WHAT THE RESEARCH TEAM PLANS TO DO WITH THE STUDY RESULTS:

For example - publish or use for dissertation

The research team intends to publish the results of the current study in peer-reviewed journals.

Section 3: Recruitment

3.1 DESCRIBE THE SUBJECT POOL, INCLUDING INCLUSION AND EXCLUSION CRITERIA AND NUMBER OF SUBJECTS:

Examples of inclusion/exclusion criteria - gender, age, health status, ethnicity

Up to 100 current cigarette smokers will be recruited from the community surrounding Roanoke, VA. Eligible participants will be 21 to 65 years old, smoke from 5 to 40 cigarettes per day, have a breath carbon monoxide (CO) level of at least 10 ppm at intake, currently use or are willing to sample nicotine pouches, and have no immediate plans to quit smoking. Females who are planning pregnancy, pregnant, lactating, not willing to use contraception during the study, and individuals who have plans to move out of the area during the course of the experiment will be excluded from participation. Use of other tobacco/nicotine products will not be exclusionary. These minimally restrictive inclusion/exclusion criteria will allow for a broad range of participants and increase the generalizability to tobacco regulation of our eventual results.

3.2 WILL EXISTING RECORDS BE USED TO IDENTIFY AND CONTACT / RECRUIT SUBJECTS?

Examples of existing records - directories, class roster, university records, educational records

No, go to question 3.3

Yes, answer questions within table

IF YES

Are these records private or public?

Public

Private, describe the researcher's privilege to the records:

Private, describe the researcher's privilege to the records:

Participants will be contacted if they have given prior permission (through a previous informed consent form) or by completion of a confidential pre-screening questionnaire.

	4
Will student, faculty, and/or staff records or contact information be requested from the	
University? No	
☐ Yes, visit the following link for further information: http://www.policies.vt.edu/index.php (policy no. 20)	010)

3.3 DESCRIBE RECRUITMENT METHODS, INCLUDING HOW THE STUDY WILL BE ADVERTISED OR INTRODUCED TO SUBJECTS:

Participants will be recruited from the community via advertisements such as posted flyers, internet (e.g., Facebook or other websites), etc. To the extent possible, we will attempt to minimize obstacles to participation. For example, travel barriers may be addressed by providing transportation or parking costs for participants, and scheduling barriers will be minimized by offering a flexible study visit schedule. Compensation may be provided for travel costs and time. All methods and measures will be conducted using standard operating procedures, and all staff (including recruitment staff) will be provided with online human subjects training. We have a history of successful recruitment of cigarette smokers into research programs. All participants will enroll on a voluntary basis.

3.4 PROVIDE AN EXPLANATION FOR CHOOSING THIS POPULATION:

Note: the IRB must ensure that the risks and benefits of participating in a study are distributed equitably among the general population and that a specific population is not targeted because of ease of recruitment.

Cigarette smokers who also currently use or would be willing to sample nicotine pouches will be recruited for this study. This population was chosen because the current experiment entails smoking cigarettes and nicotine pouches. Non-smokers would not be appropriate because nicotine and tobacco smoke may make individuals that do not regularly smoke feel ill. Women who can and may become pregnant (e.g., able to

become pregnant and planning to become pregnant or don't use contraceptives) are excluded as the current tobacco products are investigational and risks to developing fetuses are unknown. Otherwise healthy individuals are sought to minimize any ill effects that exposure to nicotine and cigarette smoke may cause.

Section 4: Consent Process

For more information about consent process and consent forms visit the following link: http://www.irb.vt.edu/pages/consent.htm

If feasible, researchers are advised and may be required to obtain signed consent from each participant unless obtaining signatures leads to an increase of risk (e.g., the only record linking the subject and the research would be the consent document and the principal risk would be potential harm resulting in a breach of confidentiality). Signed consent is typically not required for low risk questionnaires (consent is implied) unless audio/video recording or an in-person interview is involved. If researchers will not be obtaining signed consent, participants must, in most cases, be supplied with consent information in a different format (e.g., in recruitment document, at the beginning of survey instrument, read to participant over the phone, information sheet physically or verbally provided to participant).

4.1 CHECK ALL OF THE FOLLOWING THAT APPLY TO THIS STUDY'S CONSENT PROCESS:

☐ Verbal consent will be obtained from participants
Written/signed consent will be obtained from participants
Consent will be implied from the return of completed questionnaire. Note: The IRB recommends providing consent information in a recruitment document or at the beginning of the questionnaire (if the study only involves implied consent, skip to Section 5
below) ☐ Other, describe:

4.2 PROVIDE A GENERAL DESCRIPTION OF THE PROCESS THE RESEARCH TEAM WILL USE TO OBTAIN AND MAINTAIN INFORMED CONSENT:

Potential participants will be provided with the written consent form prior to visiting a Virginia Tech facility (e.g., by email), if they wish. They will also be given additional time in a quiet room in a Virginia Tech facility to read the form. Virginia Tech affiliated research staff will review each element of the written consent form with the potential participant. The potential participant will be given the opportunity to ask questions and will have as much time as they need to decide whether they would like to participate in the study. They will be encouraged to speak with whomever they wish before making this decision. Staff will reiterate that the potential participant can choose to decline participation in the study at that time or at any time thereafter without consequence. The potential participant and person obtaining consent will sign the consent form after the potential participant verbally states that s/he understands the conditions of the study, has no more questions, and chooses to participate.

4.3 WHO, FROM THE RESEARCH TEAM, WILL BE OVERSEEING THE PROCESS AND OBTAINING CONSENT FROM SUBJECTS?

Study team members that have been delegated this responsibility by the Pl.

4.4 WHERE WILL THE CONSENT PROCESS TAKE PLACE?

In a quiet room in a Virginia Tech facility.

4.5 DURING WHAT POINT IN THE STUDY PROCESS WILL CONSENTING OCCUR? Note:

unless waived by the IRB, participants must be consented before completing any study procedure, including screening questionnaires.

Consenting will occur prior to any study procedures.

4.6 IF APPLICABLE, DESCRIBE HOW THE RESEARCHERS WILL GIVE SUBJECTS AMPLE TIME TO REVIEW THE CONSENT DOCUMENT BEFORE SIGNING:

Note: typically applicable for complex studies, studies involving more than one session, or studies involving more of a risk to subjects.

Prior to visiting the lab, participants will be given the option to receive a copy of the consent form before attending a consent session. They will be able to receive the consent copy via e-mail, mail, or in person if they wish. The potential participant will be given the opportunity to ask questions and will have as much

time as they need to decide whether they would like to participate in the study. They will be encouraged to speak with whomever they wish before making this decision.

П	Not	app]	licab	le

Section 5: Procedures

5.1 PROVIDE A STEP-BY-STEP THOROUGH EXPLANATION OF ALL STUDY PROCEDURES EXPECTED FROM STUDY PARTICIPANTS, INCLUDING TIME COMMITMENT & LOCATION:

We will first ask potential participants a series of brief screening questions to determine whether they will likely meet eligibility criteria. Individuals who are eligible based on the screening questionnaire will be scheduled for an informed consent session. Note that this phone screening script is used in many studies conducted here and is a broad screening to examine eligibility in a number of ongoing studies. The phone screen script is approved in VT IRB Protocol: 13-294.

The current study will take place over at least 2 laboratory sessions at the VTC's Addiction Recovery Research Center including the consent session (approximately 1 hour). Following informed consent, participants may also be asked to leave a baseline CO sample and urine sample (females only). The urine sample will be tested for pregnancy in females. Participants will be asked the following question: "Do you actively have plans to quit smoking cigarettes within the next 30 days?" If the participant answers "Yes",

they will be excluded from participation and provided the [name] ([name]) hotline, which can connect callers to a variety of local resources for quitting. Participants will then complete approximately two laboratory sessions described below. Participants with active plans to quit may complete the assessment session but will not receive cigarettes/nicotine pouches nor return for the subsequent sessions.

Assessment session (approximately 1 hour). The first lab session will be the assessment session to collect information from participants on substance use patterns and severity, as well as the results of behavioral and cognitive tasks that we think may inform or compliment the results from the main study (see appendix for examples). This may be on the same day as the consent session.

Eligible participants will then receive two nicotine concentrations of the SPECTRUM investigational cigarette: NRC102/103 (~0.4mg/g cigarette in tobacco/menthol flavor depending upon participant's usual brand flavor) and NRC600/601 (~17.4mg/g cigarette in tobacco/menthol flavor) and two concentrations of nicotine pouch (ON! brand; 2 mg and 8 mg). Participants will receive approximately two days' worth of products to sample (based on the participant's normal amount of smoking as measured by the 30-day Timeline Followback), as well as take home assessments related to participants' subjective ratings of the products. This product sampling will include both investigational cigarettes and nicotine pouches matched to the participant's typical cigarette flavor (tobacco/menthol) and pouch flavor preferences (e.g., berry, mint).

During each day of the sampling period, participants will be contacted towards the end of the day via an Interactive Voice/Text Response service (either an automated call or automated text message) and will be asked how many of each product they used that day. This will allow more accurate daily monitoring of product usage compared to returning and retrospectively reporting their product use. We will also be able to investigate the correspondence between daily reporting and the Timeline Followback. During each IVR call, we will also ask a single question related to withdrawal feelings e.g., "On a scale of 0-9 with 0 being no withdrawal symptoms at all and 9 being extreme withdrawal symptoms, how would you rate your overall withdrawal symptoms today?"

Hypothetical Experimental Tobacco Marketplace sessions (approximately 15-30 min). Approximately 7 days following the completion of the sampling period, participants will return to the laboratory where they will bring back SPECTRUM cigarette butts and any unused products. We will ask them to complete a Hypothetical Experimental Tobacco Marketplace. During these Hypothetical Experimental Tobacco Marketplace sessions, participants will sit in front of a computer and respond to an online marketplace where they will be able to "purchase" a variety of nicotine products (e.g., investigational cigarettes, nicotine gum, snus, nicotine pouches). Importantly, the marketplace interface mimics what participants might encounter if they shopped online for these products. In order to obtain the behavioral economic measures described earlier (e.g., demand intensity, substitutability, complementarity), participants will complete a series of purchasing scenarios where the price of cigarettes (investigational cigarettes) is manipulated (approximately 6 prices) and all other nicotine products remain at a constant price. Participants will be given an allowance equal to seven days' worth of their typical expenditure on cigarettes and/or other tobacco products and will be asked to make purchases for the following seven days. Participants will be told to make these decisions as if they will actually receive the products, but participants will not actually receive the products they purchase.

The Hypothetical Experimental Tobacco Marketplace sessions will include:

- 1.Investigational cigarette A (0.4mg/g) increases in price (across separate blocks), with no other products available
- 2.Investigational cigarette B (17.4 mg/g) increases in price (across separate blocks), with no other products available
- 3. Investigational cigarette A (0.4mg/g) increases in price (across separate blocks), all other products' prices stay the same (no conventional cigarettes).
- 4.Investigational cigarette B (17.4 mg/g) increases in price (across separate blocks), all other products' prices stay the same (no conventional cigarettes).

During the last session, participants will complete several of the tasks completed during the assessment session (e.g., cigarette and nicotine pouch valuation, delay discounting tasks for hypothetical money, Timeline Followback, Fagerström Test of Cigarette Dependence).

At the end of the last session or when a participant withdraws from study, we will remind participants of the [name] hotline.

5.2 DESCRIBE HOW DATA WILL BE COLLECTED AND RECORDED:

All data will be collected and recorded with custom-built computer programs and/or standardized paper forms by trained study staff.

5.3 DOES THE PROJECT INVOLVE ONLINE RESEARCH ACTIVITES (INCLUDES ENROLLMENT, RECRUITMENT, SURVEYS)?

View the "Policy for Online Research Data Collection Activities Involving Human Subjects" at http://www.irb.vt.edu/documents/onlinepolicy.pdf

No, go to question 6.1

stions within table
IF YES
Identify the service / program that will be used:
www.survey.vt.edu, go to question 6.1
☐ Blackboard, go to question 6.1
☐ Center for Survey Research, go to question 6.1
Other
IF OTHER: Name of service / program: REDCap, Craigslist, Facebook
URL: http://www.redcap.com/, https://www.craigslist.org/, https://www.facebook.com This service is
☐ Included on the list found at: http://www.irb.vt.edu/pages/validated.htm ☐ Approved by VT IT Security
☐ None of the above (note: only permissible if this is a collaborative project in which VT individuals are only responsible for data analysis, consulting, or recruitment)

Section 6: Risks and Benefits

6.1 WHAT ARE THE POTENTIAL RISKS (E.G., EMOTIONAL, PHYSICAL, SOCIAL, LEGAL, ECONOMIC, OR DIGNITY) TO STUDY PARTICIPANTS?

One risk of participation is embarrassment that may come from answering sensitive questions related to medical, psychiatric, and/or drug use history. Loss of confidentiality is another risk of participation. Finally, there may be the potential for increased withdrawal symptoms related to less than usual nicotine intake.

Participants will be screened, using medical history and structured interviews, for a history of medical contraindications (e.g., pregnancy), and current unstable medical illnesses. The study will occur in one of our Virginia Tech facilities. Participants will be free to withdraw from the study at any time, and their refusal to continue will not affect other medical care associated with Carilion. Participants will be told that a risk may include increased withdrawal symptoms related to less than usual nicotine intake. In addition, if participants develop medical problems or experience adverse events during the course of the study, assessments to determine whether participants should continue in the study and/or continue to use study products will be conducted and necessary referrals will be provided. Using only ID numbers and keeping all data in secure locations and/or in locked offices accessible only to trained study team members will protect confidentiality. Computer databases will have coded identifiers. These screening, monitoring, and confidentiality procedures have been in effect for more than 10 years and for more than 2,000 subjects across the various protocols employed by our group across various institutions.

6.3 WHAT ARE THE DIRECT OR INDIRECT ANTICIPATED BENEFITS TO STUDY PARTICIPANTS AND/OR SOCIETY?

Participants might benefit from education about research participation. The project invoves minimal risk to confidentiality or other personal rights or to physical or emotional health. Thus, the expected benefits outweigh the very minimal risks to participants.

Section 7: Full Board Assessment

☐ Prisoners

☐ Mentally disabled persons

7.1 DOES THE SEDATION?	RESEARCH INVOLVE MICROWAVES/X-RAYS, OR GENERAL ANESTHESIA OR
No ⊠	
☐ Yes	
	RCH ACTIVITIES INVOLVE PRISONERS, PREGNANT WOMEN, FETUSES, FRO FERTILIZATION, OR MENTALLY DISABLED PERSONS?
No, go to question	n 7.3
☐ Yes , answer ques	tions within table
	IF YES
	This research involves:

☐ Human in vitro fertilization

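### Section 5.1 words the baseline CO and urine samples as optional, which is inconsistent with the CO criterion in 3.1 and lets the pregnancy exclusion rest on history and interview alone

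*Protocol*

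**What the plan says.** Section 3.1 sets the entry criteria. Participants must "have a breath carbon monoxide (CO) level of at least 10 ppm at intake". Among those excluded are "Females who are planning pregnancy, pregnant, lactating, not willing to use contraception during the study".

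Section 5.1 describes what happens after consent: "participants may also be asked to leave a baseline CO sample and urine sample (females only". Urine that has been collected is then definitely tested for pregnancy; the permissive wording applies to collection only. Later in 5.1, two strengths of investigational cigarette and two strengths of nicotine pouch are given to participants who are eligible. Neither a CO value nor a pregnancy result is named at that step. People with active plans to quit may complete the assessment session but receive no products.

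Section 3.4 explains the pregnancy-related exclusion: "the current tobacco products are investigational and risks to developing fetuses are unknown". The Section 6 text on protecting participants, between 6.1 and 6.3, adds screening by medical history and structured interview and gives pregnancy as an example of what is looked for.

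**The concern.** A numerical entry criterion can be applied only to someone who has been measured. If the measurement is optional on paper, the record may not show that each participant met the criterion, and two members of staff could reasonably read their duty differently.

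For pregnancy the stake is safety. History and interview can find only what a woman knows and chooses to report. The 3.1 exclusions for planning a pregnancy or declining contraception concern intentions, so they do not detect an early pregnancy that already exists. A urine test could detect one, and the protocol has one in hand, but does not commit to collecting the sample.

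**Working it through.** No arithmetic applies. The only figure involved is the 10 ppm threshold, which appears once, in 3.1. The check compares the relevant sections.

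**CO**
1. Criterion: 3.1 requires 10 ppm or more at intake.
2. Source of the reading: the sentence in 5.1 is the only collection step in the supplied text. The pre-consent screen is a telephone questionnaire and cannot yield a breath reading, and 4.5 places consent before every study procedure.
3. Strength of the wording: collection is *may*. In the same paragraph the quit-plan question and the testing of collected urine are both *will*.
4. Dispensing: 5.1 limits it to eligible participants, and by step 1 eligibility includes the CO threshold.
5. Result: steps 1 and 4 together imply that a reading must exist before dispensing, and step 3 does not require one. The sections are inconsistent.

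**Pregnancy**
1. Criterion: 3.1 excludes pregnant women and does not say how pregnancy is to be established.
2. Sources of information: the history and interview screen in Section 6, which is stated firmly, and the urine test in 5.1, whose collection is optional.
3. Dispensing: a woman who passes the interview can be treated as eligible with no test, and no sentence is breached.
4. Result: there is no contradiction, but the written text permits dispensing on self-report alone.

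**What exposure is added**

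These women already smoke (3.1: "smoke from 5 to 40 cigarettes per day"), so the study cigarettes may largely replace their usual ones. The pouches may be a new exposure, because 3.1 admits people who "currently use or are willing to sample nicotine pouches".

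**The case against.** The strongest reply is that the protocol must be read as a whole. A reader might infer from 5.1 that staff are free to dispense products with no CO reading. The documents do not support that: the dispensing step sits in the same section and is confined to eligible people, and someone without a reading has not been shown to be eligible. The closing statement of the protocol binds staff to all of it, including 3.1, so one *may* does not override an entry criterion. This stands, and it limits the CO point to an inconsistency in wording.

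The *may* could also describe when the samples are taken, since the assessment session can fall on a later day. It could allow for people with quit plans or women who cannot become pregnant. Either is possible, but the text says neither, and the heading of 5.1 asks the author to "PROVIDE A STEP-BY-STEP THOROUGH EXPLANATION OF ALL STUDY PROCEDURES EXPECTED FROM STUDY PARTICIPANTS".

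On pregnancy, the reply is that a mandatory test adds a safeguard and corrects no error. That is right. It is also fair that 2.1 describes the pouches as commercially available, whereas the reason in 3.4 rests on the products being investigational, so that reason fits the cigarettes more directly.

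Finally, section 3.3 says "All methods and measures will be conducted using standard operating procedures". Those procedures, the consent form and the appendix are not among the supplied documents and may already require both samples. The point therefore concerns the supplied text only.

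**Conclusion.** The point holds in two parts of different weight. For CO, 5.1 fails to require a reading that 3.1 and the dispensing step together imply; this is an internal inconsistency. For pregnancy, the text leaves a gap that a planned test could largely close; this is a safety improvement. A reader might infer that the protocol contradicts itself on pregnancy, but 3.1 never requires a test, so it does not.

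Nor can it be inferred that ineligible or pregnant people will in fact receive products. The CO sample concerns up to 100 participants and the urine test the women among them, but the documents give neither the share who would not be asked nor the share of women. No number affected is claimed. No sample size, power or analysis figure depends on the point.

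The conclusion assumes that *may* carries its ordinary permissive meaning and that nothing outside the supplied text makes the samples mandatory. On that basis the wording should be changed.

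**What to change.** In 5.1, replace *may* with *will* for both samples, for everyone who is to receive products. At the dispensing step, state that products are released only after a recorded CO of 10 ppm or more and, for females able to become pregnant, a negative urine pregnancy test. State that people with active quit plans, who complete only the assessment session and receive no products, are exempt.

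The cost is a short amendment, submitted for IRB approval, and the sampling of every participant who receives products. If the standard operating procedures already require both samples, only the wording changes.
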